2.3.2 Secondary endpoints/outcomes

- Proportion of participants with plasma HIV-1 RNA <50 c/mL at week 24, 48 and 96.
- Changes in laboratory parameter from baseline.
- Changes in renal markers, bone markers, and fasting lipids from baseline at week 24, 48 and 96.

CONFIDENTIAL

- Resistant outcomes in failures (descriptive analysis) and baseline factors associated with failure i.e. treatment emergent mutations (NRTI, NNRTI, PI and II regions) as compared with previous resistance tests.
- Changes in QoL and patient satisfaction from baseline.
- Number of participants with adverse events (AEs), severity of AEs, and treatment discontinuations due to AEs.
- Number of potential DDIs avoided (This will be measured by comparing the drug interaction outcomes between antiretroviral therapy and co-medications before and after the switch by using the www.hiv-druginteractions.org/ website (within the same study arm and between study arms). The grading will be done by looking at how many interactions graded amber or red will be graded green after the switch. For example, if a patient on atorvastatin as a co-medication and on two NRTIs and darunavir/cobicistat he would score “one amber and two green” and when switched to rilpivirine/dolutegravir, he would score “all green”, showing the latter regimen is more favourable in terms of drug-drug interactions).
- Virological suppression (<200 copies/ml HIV RNA) at week 24, 48, 96 in individuals with previous NNRTIs virological failure and/or baseline transmitted resistance with the k103N resistance mutation, switching to DTG/RPV FDV. Analysed in line with FDA Snapshot method.
- Pre-dose plasma concentrations of DTG and RPV at week 4 (experimental arm only), 48 (experimental arm only) & 96. Plus pre/post-dose (as appropriate) at early termination visit and /or in the event of virological failure (see section 6.12) a post dose sample will be taken within 20-28 hours.
- Changes in cell associated virus using PBMC Illumina MiSeq sequencing at week 48 and week 96.

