6.15 Decline in Renal Function

Subjects who experience an increase in creatinine from Baseline of 45 mMol/L (or 0.5 mg/dL) without associated evidence for proteinuria should return for a confirmatory assessment within 2 to 4 weeks. A urinalysis and urine microalbumin/creatinine ratio should be done at this confirmatory visit. If the creatinine increase is confirmed, the investigator should contact the sponsor to discuss additional follow-up and medical management.

Subjects who have a decline in creatinine clearance of >50% must return for a confirmatory assessment as soon as possible. A urinalysis and urine microalbumin/creatinine ratio should be done at this confirmatory visit. If the estimated creatinine clearance has declined by >50% (confirmed), then study medication should be withheld and the investigator should contact the sponsor to discuss the rationale for restarting study drugs (if appropriate). Consideration for confounding factors (e.g. NRTI background therapy, other medications, dehydration, concurrent conditions) should be taken into account, and a nephrology consult may be obtained. If a subject in the control group is also receiving TDF, then a switch to an alternative fully active NRTI should be considered if restarting study medication. Current local prescribing information should be consulted for additional details on dosing background therapy in renally impaired subjects. If study medication is reinitiated, it should have been withheld for no more than 4 weeks. If IP is not reinitiated the subject must be withdrawn.

Proximal Renal Tubule Dysfunction (PRTD) is defined as:

- Confirmed rise in serum creatinine of ≥ 0.5 mg/dL from baseline AND serum phosphate < 2.0 mg/dL;
- Either of the above accompanied by any two of the following:

CONFIDENTIAL

- Glycosuria (≥ 250 mg/dL) in a non-diabetic;
- Low serum potassium (< 3 mEq/L);
- Low serum bicarbonate (< 19 mEq/L).

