3.2 Study endpoints

3.2.1 Primary endpoint/outcome

The primary endpoint is the proportion of participants free of therapeutic failure at week 48 (HIV RNA <50 copies/mL and no discontinuation). Therapeutic failure is defined as virologic failure or discontinuation with HIV RNA <50 copies/mL. Discontinuation is defined by the study follow-up stop or any change or modification in the study treatment regimen.

The following procedure will be used to classify the participants.

1. Virological failure:

- (a) Any patient with HIV RNA levels ≥ 50 copies/mL at any time points will have a repeat test on a second measurement within 2 weeks apart. If the result from the second measurement is <50 copies/mL, the patient will be categorized as HIV-RNA <50 copies/mL. If the result from the second measurement is ≥ 50 copies/mL, the patient will be categorized as virological failure.
- (b) If a patient has HIV-RNA ≥ 50 copies/mL at a given time point and stops the study or at least one drug from the study treatment combination for any reason, he or she will be categorized as virological failure.
- (c) If a patient discontinues the study or at least one drug from the study treatment combination at a given time point because of lack of efficacy then the patient will be categorized as virological failure.

2. Discontinuation (no virological data)

All discontinuations with HIV RNA <50 copies/mL will be considered as no virological data. There are three main reasons for no data at analysis time point:

- (a) Discontinuation due to Adverse Event (AE) or Death.

Any patient who discontinues the study or the study treatment with HIV-RNA is < 50 copies/mL because of AE or death will be classified as discontinuation due to AE or death at from the date of discontinuation.

(b) Discontinuation for Other Reasons.

If a patient discontinues the study follow-up or changes or modifies any drug in the study treatment when his or her HIV-1-RNA is < 50 copies/mL, he or she will be categorized as discontinued for other reasons at from the date of discontinuation.

(c) On study but missing data at analysis time point.

For example, if a participant has no data at analysis time point, but there is an HIV-RNA measurement after the analysis time point, this patient will be considered On Study but with Missing Data at analysis time point.

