3.2.2 Secondary endpoints/outcomes

Secondary endpoints will include secondary efficacy endpoints, secondary safety endpoints, pharmacological endpoints, and secondary endpoints regarding patient related outcomes.

Secondary efficacy endpoints:

- (a) Proportion of participants with virological failure (2 consecutive viral loads > 50 copies at least 2 weeks apart or a viral load > 50 copies/mL followed by a discontinuation of the study or the study treatment), investigated over 96 weeks.
- (b) Incidence of genotypic resistance in case of confirmed HIV RNA > 50 copies/mL and baseline factors associated with failure i.e. treatment emergent mutations (NRTI, NNRTI, PI and II regions) as compared with previous resistance tests.
- (c) Proportion of participants with plasma HIV-1 RNA < 50 c/mL at week 24, 48 and 96.
- (d) Proportion of participants with virological suppression (< 200 copies/ml HIV RNA) at week 24, 48, 96
- (e) Changes from baseline in cell associated virus using PBMC Illumina MiSeq sequencing at week 48 and week 96.
- (f) Changes from baseline in CD4, CD8 and CD4/CD8 ratio over 96 weeks with evaluation at week 24, 48 & 96.

Secondary safety endpoints:

- (g) Number and percentage of participants with adverse events (AEs), severity of AEs, and treatment discontinuations due to AEs.
- (h) Changes from baseline in laboratory parameter at week 24, 48 and 96.
- (i) Changes from baseline in renal markers, bone markers, and fasting lipids at week 24, 48 and 96.

Secondary endpoints regarding pharmacological outcomes:

- (j) Pre-dose plasma concentrations of DTG and RPV at week 4 (experimental arm only), 48 (experimental arm only) & 96. Plus pre/post-dose (as appropriate) at early termination visit and /or in the event of virological failure a post dose sample will be taken within 20-28 hours.

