7.2 Protocol Deviations

The following violations are defined as protocol deviations for the purpose of analysis: The deviation might be related to:

- (a) Eligibility;
- (b) Study related assessments;
- (c) Social history;
- (d) PK sampling;
- (e) Drug dispensing;
- (f) Adherence;
- (g) Follow up (lost to follow-up,);
- (h) Other (consent withdrawal, giving up, ...)

The following violations will be considered as a serious deviation for the purpose of analysis: Patients who will not take study treatment; Interruptions of study drug for >10% of total time on treatment; Patient who will not fulfil the eligibility criteria; Patients who will withdraw the consent; Patients who will not comply with their randomization arm; Patients with missing value at the primary endpoint evaluation: Patient who will be lost to follow-up.

A patient will be considered lost to follow-up when he/she will not come to more than 2 visits of the

protocol. Patients who cannot be contacted on or before the last scheduled visit prior to the week 96 and who will not have a known reason for discontinuation (eg, withdrew consent, giving up, etc.) will be classified as “lost to follow-up”.

Patients will be considered in discontinuation of the study when they will refuse to continue the follow-up of the study.

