8.2.2 Immunological evaluation

(f) Change from baseline in CD4, CD8, and CD4/CD8 ratio over 96 weeks with evaluation at week 24, 48, and 96.

The evolution of the CD4, CD8 and CD4/CD8 ratio over 96 weeks according to the treatment group will be described by boxplots for each treatment group at each visit. The changes will also be compared between the two treatment group using mixed models for repeated measures with random intercept and unstructured covariance matrix, adjusted for baseline value. The models will include treatment group, time, interaction between treatment group and time, and baseline value. Time will be considered as categorical variable (0, 12, 24, 48, 72 and 96 weeks) according the planned study visits. Visits window are shown in Table A (section 6.2). Data will be also summarised in tables by mean and standard error.

If the residual of the mixed model is not normally distributed and therefore does not allow the use of parametric test, the changes from baseline to week 24, 48 and 96 of CD4 T cell count, CD8 T cell count and CD4/CD8 ratio will be compared between the 2 groups using Mann-Whitney-Wilcoxon test.

9. Safety analyses:

(g) Number and percentage of participants with adverse events (AEs), severity of AEs, and treatment discontinuations due to AEs.

Adverse events (AE), especially grade 3 and 4 AE, serious adverse events (SAE), drug-related AE (all grades), treatment interruption due to AE (all grades), pregnancies and death will be summarized with descriptive statistics. The incidence rates of the events defined above will be compared between the treatment groups using a Poisson regression analysis which accounted for all adverse events and follow-up duration for each participant. The Poisson regression models will include the number of events, the treatment group and the duration of exposure in year in log. The number and percentage of death as well as the causes of death will be given. The number and percentage of pregnant women will also be given. A table will summarize the frequency of adverse events and pregnancies. This table will include the name of event, number and percentage of patients with events, number of events, and incidence rate (IR) per 100 person-years in the DTG/RPV group and the control group respectively, and incidence rate ratio (IRR) and 95%CI for IRR. All grades 3 or 4 AE related to the study drugs and treatment interruption due to AE will be put in the table.

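### SAP 9(g) analyses treatment interruption due to adverse events, while the endpoint it serves is treatment discontinuation due to adverse events

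*SAP*

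**What the plan says.** The endpoint is stated the same way in both documents. Protocol 2.3.2 lists "Number of participants with adverse events (AEs), severity of AEs, and treatment discontinuations due to AEs". SAP 3.2.2(g) lists "Number and percentage of participants with adverse events (AEs), severity of AEs, and treatment discontinuations due to AEs", and SAP section 9 opens item (g) with that same line as its heading.

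The text under the heading uses a different word. Its list of events ends with "treatment interruption due to AE (all grades), pregnancies and death will be summarized with descriptive statistics". The comparison then refers back to that list: "The incidence rates of the events defined above will be compared between the treatment groups using a Poisson regression analysis". On the results table it says: "All grades 3 or 4 AE related to the study drugs and treatment interruption due to AE will be put in the table". The table is to show participants with events (number and percentage), number of events, incidence rate per 100 person-years, and the incidence rate ratio with its 95% CI. Discontinuation does not appear in this text, and interruption is not defined.

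**The concern.** In a trial of switching suppressed patients to a simpler regimen, the share who stop that regimen because of AEs is a main measure of tolerability. The documents treat it so: protocol 9.6 and SAP 6.6 both list a high rate of AE discontinuation among the issues for interim decisions. If the analysis counts interruptions, the reported figure answers another question, namely how often dosing was broken for an AE, whether or not treatment resumed. The unit also changes. A Poisson model of events can count several interruptions in one participant, whereas stopping the regimen is in practice a single event per participant.

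**Working it through.** The documents state no rate, power or sample size for AE discontinuation or interruption, so there is no figure to reproduce. The check is mainly a comparison of text.

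**1. Endpoint against analysis**

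| Place | Event named |
|---|---|
| Protocol 2.3.2 | discontinuation |
| SAP 3.2.2(g) | discontinuation |
| SAP 9(g), heading | discontinuation |
| SAP 9(g), events summarised and compared | interruption, all grades |
| SAP 9(g), contents of the table | interruption |

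**2. Are the two words synonyms in these documents?**

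- Protocol 6.12, in its text on rash, names interruption and discontinuation side by side as alternatives.
- SAP 7.2 counts as a serious deviation "Interruptions of study drug for >10% of total time on treatment". A share of time on treatment describes a gap in dosing, not an end to it.
- Protocol 6.13 orders an immediate hold and then separates two outcomes: permanent discontinuation, or possible restart when there is a clear alternative cause.
- Protocol 6.15 also allows a hold with restart: "If study medication is reinitiated, it should have been withheld for no more than 4 weeks".
- SAP 3.2.1 defines discontinuation for the primary endpoint ("Discontinuation is defined by the study follow-up stop or any change or modification in the study treatment regimen") and does not mention interruption.

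**3. What each reading would deliver**

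- Temporary gaps only: the named endpoint is not analysed.
- Any break in treatment: restarted holds and stops are mixed in one count.
- A slip for discontinuation: the endpoint is analysed, but the text does not say so.

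**4. Does another section supply the arm comparison?**

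- SAP 3.2.1, item 2(a), classifies discontinuation for AE or death only when HIV RNA is below 50 copies/mL. Under item 1(b), a participant at 50 or above who stops for any reason is a virological failure. The category can therefore miss AE stops.
- SAP 7.1 reports reasons for discontinuing the study, which SAP 7.2 describes as refusing further follow-up. Protocol 6.12 asks participants who stop medication to keep attending to week 96, so an AE stop need not appear there.
- Protocol 9.2.2 has a category for missing HIV RNA after an AE discontinuation, and protocol 9.5 counts AE or death discontinuations at the interim. Neither is a between-arm safety analysis.

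**5. How sensitive a rate ratio would be (all rates assumed)**

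Take the planned 100 and 50 participants, full follow-up to week 48 and one event per participant. Person-years are 100 × 48/52 = 92.3 and 50 × 48/52 = 46.2. Let the true discontinuation proportion be the same in both arms. Then IRR = (e1/92.3)/(e0/46.2), with SE of log IRR = √(1/e1 + 1/e0).

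IRR if restarted holds occur only in the DTG/RPV arm:

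| Discontinuation, both arms | no holds | 1% | 2% | 3% | 5% |
|---|---|---|---|---|---|
| 2% | 1.00 | 1.50 | 2.00 | 2.50 | 3.50 |
| 4% | 1.00 | 1.25 | 1.50 | 1.75 | 2.25 |
| 6% | 1.00 | 1.17 | 1.33 | 1.50 | 1.83 |

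Example, 4% with 2% holds: e1 = 6, e0 = 2, SE = √(1/6 + 1/2) = 0.816, 95% CI 0.30 to 7.43. Every interval in the table includes 1.

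With the same proportion of holds in both arms, the IRR stays at 1.00. With 4% discontinuation and 2% holds in the control arm only, e1 = 4, e0 = 3 and IRR = (4/92.3)/(3/46.2) = 0.67. The answer depends wholly on where the holds fall, and the documents do not say.

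**The case against.** The best defence is that interruption is loose wording. The paragraph sits under a heading that says discontinuation, and its table gives number and percentage of participants, as the endpoint requires. This reading is possible and may be what was meant. It is not established, because both documents elsewhere use interruption for something else and SAP 9(g) leaves it undefined.

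Three further points stand in part. The gap between the two counts may be small: under protocol 6.13 the drugs must be stopped permanently if a causal link cannot be ruled out, restart needs several approvals and fresh consent, and under 6.15 a participant who does not restart is withdrawn. Only restarted participants separate the two counts. AE stops are also partly visible elsewhere, as step 4 shows, though not compared between arms. And this is a secondary safety summary in a self-described pilot.

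A reader might go further and infer that the wording biases the comparison against DTG/RPV, because the hold rules are written for those drugs. The documents do not support that. Only the liver rule in 6.13 names dolutegravir and rilpivirine. The renal rule in 6.15 speaks of study medication and addresses control participants, and 6.12 lets investigators stop medication for toxicity without restriction by arm. After week 48 the control arm takes DTG/RPV as well.

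**Conclusion.** The mismatch holds on the text and needs no assumed rate: the endpoint names one event and the analysis another. Followed literally, SAP 9(g) gives no between-arm analysis of AE discontinuation and counts reversible holds together with stops. Neither the size nor the direction of any effect on the comparison can be derived; the rate ratios above only show that, at event counts this low, a few holds could move the estimate noticeably. The primary efficacy analysis is not affected. The point is worth correcting because the endpoint matters to the trial's question and the correction is nearly free.

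**What to change.** In SAP 9(g), replace the interruption term in both places where it occurs (the list of events and the contents of the table) with *discontinuation of the study treatment regimen due to AE*. Report it as number and percentage of participants by arm, including the randomised comparison to week 48, before the control arm switches. Report temporary interruptions that were restarted as a separate descriptive line. Add one sentence on how the SAP 3.2.1 definition applies here, so that a restarted hold is counted on one line only.

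The cost is SAP wording. No new data are needed, since protocol 6.12 already requires the date and reasons for stopping medication on the CRF. No clinical rule changes.

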
DTG & RPV: Drug induced liver injury (DILI) and other clinically significant liver chemistry elevations
	
DTG: Non-clinical data suggested a possible, albeit low, risk for hepatobiliary toxicity with DTG. Drug-related hepatitis is considered an uncommon risk for ART containing DTG regardless of dose or treatment population. For subjects with hepatitis B virus (HBV) and/or hepatitis C virus (HCV) co-infection, improvements in immunosuppression as a result of HIV virologic and immunologic responses to DTG- containing ART, along with
	
Subjects meeting either of the following criteria during the screening period are excluded from participating.
 
 • Alanine aminotransferase (ALT) ≥ 5 times the upper limit of normal (ULN) or ALT $\geq 3 \times$ULN and bilirubin $\geq 1.5 \times$ ULN (with $>35\%$ direct bilirubin) • Subjects with acute viral hepatitis • Subjects positive for Hepatitis B surface antigen (+HBsAg) at screening

CONFIDENTIAL

Potential Risk of Clinical Significance	Data/Rationale for Risk	Mitigation Strategy
Investigational Product (IP) [DTG/RPV FDC] Refer to individual IBs for DTG and RPV and the Juluca SmPC for additional information		
	
inadequate therapy for HBV co-infected subjects, are likely contributed to significant elevations in liver chemistries.
 
RPV: Hepatic events have been reported in patients receiving a RPV containing regimen. Patients with underlying HBV, HCV, or marked elevations in transaminases prior to treatment may be at increased risk for worsening or development of transaminase elevations with use of RPV. A few cases of hepatic toxicity have been reported in patients receiving a RPV containing regimen who had no pre-existing hepatic disease or other identifiable risk factors.
 
Hepatotoxicity is considered a risk for both DTG and RPV. Based on clinical trial data, synergistic or additive hepatotoxicity is not expected with DTG + RPV FDC.
	
 Subjects with an anticipated need for HCV therapy during the study. 
Specific detailed liver stopping criteria and toxicity management guidance is provided for suspected DILI or other clinically significant liver chemistry elevations (Section 6.13).

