25. Screening blood result with any grade 3/4 toxicity according to Division of AIDS (DAIDS) grading scale, except: asymptomatic grade 3 glucose, amylase or lipid elevation, asymptomatic grade 4 triglyceride elevation (re-test allowed) or unconjugated hyperbilirubinaemia due to atazanavir exposure.
26. Any condition (including illicit drug use or alcohol abuse) or laboratory results which, in the investigator's opinion, interfere with assessments or completion of the trial.
27. Women planning pregnancy or who are pregnant or breast feeding. (NB: See section 6.12 Withdrawal Criteria for guidance if pregnancy does occur).
28. Females of childbearing potential and males must be willing to use a highly effective (acceptable effective contraceptive measures are only acceptable for IMP's with unlikely human teratogenicity /

CONFIDENTIAL

fetotoxicity in early pregnancy) method of contraception (hormonal method of birth control; true abstinence). Contraceptive methods that can achieve a failure rate of less than 1% per year when used consistently and correctly are considered as highly effective birth control methods (see Appendix 4).

Such methods include:

- combined (estrogen and progestogen containing) hormonal contraception associated with inhibition of ovulation:
 - oral
 - intravaginal
 - transdermal
- progesteron-only hormonal contraception associated with inhibition of ovulation
 - oral
 - injectable
 - implantable
- Intrauterine device (IUD)
- Intrauterine hormone-releasing system (IUS)
- bilateral tubal occlusion
- vasectomised partner
- true sexual abstinence

(NB: See section 6.12 Withdrawal Criteria for guidance if pregnancy does occur).

29. Hypersensitivity to the active substances or to any of the excipients listed below:

List of excipients

Tablet core

- Mannitol (E421)
- Magnesium stearate
- Microcrystalline cellulose
- Povidone (K29/32)
- Sodium starch glycolate
- Sodium stearyl fumarate
- Lactose monohydrate
- Croscarmellose sodium
- Povidone (K30)
- Polysorbate 20
- Silicified microcrystalline cellulose

Tablet coating

- Polyvinyl alcohol- part hydrolysed
- Titanium dioxide (E171)
- Macrogol
- Talc
- Iron oxide yellow (E172)
- Iron oxide red (E172)

CONFIDENTIAL

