7 TRIAL MEDICATION

7.1 Name and description of investigational medicinal product(s)

Subjects will discontinue their usual boosted protease inhibitor or other ARV regimen (including Anatomical Therapeutic Chemical Classification System codes: JO5AB, JO5AE, JO5AF, JO5AG, JO5AR, JO5AX) and will switch to DTG plus RPV at baseline or week 48.

ViiV will supply Dolutegravir 50mg / Rilpivirine 25mg FDC tablets in the form of “Juluca” (which will be labelled in accordance with annex 13 requirements).

From baseline to week 96 or from week 48 to week 96, as randomised, participants will take a DTG/ RPV combined tablet once a day orally. Participants in the deferred group will continue to take their usual ARV regimen from baseline to week 48 until they switch to DTG/ RPV combined tablet.

The early switch group will be dispensed a supply of DTG/RPV combined tablets at baseline, week 4, 12 and 24. Both the early switch group and deferred switch group will be dispensed supply of DTG/RPV combined tablets at week 48, 52 and 72. Please refer to the study specific pharmacy manual for more information. Note, dispensing weeks may be modified with sponsor’s approval and in line with local regulations (if required). Prior to switch subjects will continue to be dispensed standard care boosted protease inhibitor or other ARV regimen.

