(h) Changes from baseline in laboratory parameters at week 24, 48 and 96.

The evolution of haematology parameters (including haemoglobin, white cell count and differential, platelets) and biochemistry parameters (including sodium, glucose, ALT, AST, and total bilirubin) according to the treatment group will be described by boxplots for each treatment group at baseline, week 24, 48 and 96. The changes from baseline will be compared between the two treatment groups

using mixed models for repeated measures with random intercept and unstructured covariance matrix adjusted for baseline value. The model will include treatment group, time and interaction between treatment group and time, and baseline value. Time will be considered as categorical variables. Data will be also summarised in tables by mean and standard error.

If the residual of the mixed model is not normally distributed and therefore does not allow the use of parametric test, the non-parametric Mann-Whitney-Wilcoxon test will be used to compare the changes from baseline to week 24, 48 and 96 between the two treatment groups.

(i) Changes from baseline in renal markers, bone markers, and fasting lipids at week 24, 48 and 96.

The evolution of renal markers (including blood creatinine, blood creatinine clearance (eGFR), urine creatinine, urine protein, urine protein/creatinine ratio, blood albumin, urine albumin, urine albumin/creatinine ratio, urine beta 2 microglobulin, urine creatinine clearance (eGFR), potassium, blood phosphate, urine phosphate), bone markers (including ALP) and lipids fasting parameters (including total cholesterol, HDL, LDL, triglycerides) according to the treatment group will be described by boxplots for each treatment group at baseline, week 24, 48 and 96.

The changes from baseline will be compared between the two treatment groups using mixed models for repeated measures with random intercept and unstructured covariance matrix adjusted for baseline value. The model will include treatment group, time and interaction between treatment group and time, and baseline value. Time will be considered as categorical variables. Data will be also summarised in tables by mean and standard error.

If the residual of the mixed model is not normally distributed and therefore does not allow the use of parametric test, the non-parametric Mann-Whitney-Wilcoxon test will be used to compare the changes from baseline to week 24, 48 and 96 between the two treatment groups.

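### SAP 9(h): at weeks 24 and 48 the between-arm change in total bilirubin mixes atazanavir withdrawal with any hepatic effect of DTG/RPV

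*SAP*

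**What the plan says.** SAP section 9(h) names "biochemistry parameters (including sodium, glucose, ALT, AST, and total bilirubin" among the laboratory parameters whose change from baseline is compared between arms at weeks 24, 48 and 96. On the model it says: "The model will include treatment group, time and interaction between treatment group and time, and baseline value". If the residuals are not normal, "the non-parametric Mann-Whitney-Wilcoxon test will be used to compare the changes from baseline to week 24, 48 and 96". Boxplots by arm and tables of means and standard errors are also required.

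Protocol section 5.2, criterion 25, excludes grade 3/4 screening results, but one of its exceptions is "unconjugated hyperbilirubinaemia due to atazanavir exposure". Protocol section 7.1 states "Subjects will discontinue their usual boosted protease inhibitor or other ARV regimen" on switching, at baseline or week 48 as randomised. For the control arm it adds: "Participants in the deferred group will continue to take their usual ARV regimen from baseline to week 48".

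Nothing in 9(h) restricts, stratifies or adjusts for atazanavir. The nearest covariate, PI at baseline (yes/no) in SAP section 6.4.2, belongs to the efficacy adjustment and is not specific to atazanavir. Baseline antiretroviral treatment is recorded and described (SAP section 7.3).

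**The concern.** The protocol itself attributes this hyperbilirubinaemia to atazanavir. Up to week 48 that cause is removed in one arm and kept in the other. Among atazanavir users, bilirubin falls on DTG/RPV and stays raised in control, for a reason that says nothing about liver injury.

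The protocol's risk table states "Hepatotoxicity is considered a risk for both DTG and RPV", so a reader will look at bilirubin for hepatic information. A pooled mean that shows improvement, or no difference, could be taken as reassurance when it reflects atazanavir withdrawal.

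**Working it through.** **Plan's own figure.** The documents state no bilirubin figure (no atazanavir share, level, variance or effect), so there is nothing to reproduce.

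**Inputs from the documents.** 100 DTG/RPV and 50 control participants (SAP section 5); model terms and fallback test (SAP 9(h)); timing of the switch (Protocol 7.1).

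**Assumed inputs.** Atazanavir share f = 5%, 10% or 20%. Mean baseline bilirubin is 30 or 50 µmol/L in atazanavir users and about 8 in others, so the fall on stopping is D = 30 − 8 = 22 or 50 − 8 = 42. The true rise due to DTG/RPV is s = +2 µmol/L.

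**1. Mean comparison at weeks 24 and 48.** The expected between-arm difference in mean change is s − f × D.

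| f | D = 22 | D = 42 | Simulated model estimate (30 / 50 µmol/L) |
|---|---|---|---|
| 5% | 2 − 1.1 = +0.9 | 2 − 2.1 = −0.1 | +1.05 / +0.27 |
| 10% | 2 − 2.2 = −0.2 | 2 − 4.2 = −2.2 | 0.0 / −1.84 |
| 20% | 2 − 4.4 = −2.4 | 2 − 8.4 = −6.4 | −2.28 / −6.10 |

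The last column is the mean over 1,500 simulated trials per cell, regressing change on arm and baseline value. The rise is fully cancelled in the mean at f = s/D, that is 2/22 = 9.1% or 2/42 = 4.8%.

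**2. Why the baseline covariate does not help.** Randomisation already balances expected baseline bilirubin, so adjusting for it hardly moves the expected difference. The imbalance is in what happens afterwards: high-baseline participants fall in one arm and not in the other. One common slope cannot represent that.

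**3. A second set of assumptions.** Others have median bilirubin 0.5 × ULN, the median fall on stopping is 2 × ULN and the true rise is +0.10 × ULN. The model estimate is +0.10 with no atazanavir users, +0.01 at 5%, −0.10 at 10% and −0.32 at 20%. The pattern is the same.

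**4. The fallback test.** The subgroup that shifts the mean also makes the residuals non-normal. Using Shapiro-Wilk (the SAP names no test), normality was rejected in 76–100% of simulated trials, so the rank test would usually apply. With the true +2 rise:
- It gave a significant fall in at most 0.3% of trials.
- With within-person SD 2.5 µmol/L, it detected the rise in about 70%, 44% and 5% of trials at shares of 5%, 10% and 20%.
- Less noise helps. With SD 1.5 or 2.5, detection ranged over 68–99%, 44–95% and 6–51%. On the ULN-scale assumptions it was 98%, 89% and 24%.

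With no true effect, the rank test gave a false fall in about 15% of trials at a 10% share and 50% at 20%. The nominal rate in that direction is 2.5%.

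**5. Participants not on atazanavir.** The same model returns +2.0. At SD 2.5, detection was 88–94%. By hand, for an unadjusted comparison, the SD of change is 2.5 × √2 = 3.54. With 95 v 47.5 participants (5% removed) the SE is 3.54 × √(1/95 + 1/47.5) = 0.63 and power is Φ(2/0.63 − 1.96), about 89%. With 80 v 40 (20% removed) the SE is 0.685 and power about 83%. Dropping the atazanavir users therefore costs little.

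**6. Week 96.** Both arms have by then left their previous regimen, so −f × D applies to both and largely cancels.

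**The case against.** **The written plan does not stop at the linear model.** This stands, and it limits the claim. A reader might infer from step 1 that the trial would report a significant bilirubin fall on DTG/RPV despite a true rise. The linear model taken alone does that in most trials at a 20% share, but the SAP sends non-normal residuals to a rank test, which almost never reverses the sign. The boxplots would also show the high-baseline cluster. What remains is lost power, some false falls when there is no effect, and tables of means that carry the artefact whichever test is used.

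**Liver injury is not judged from mean total bilirubin.** This also stands. A reader might infer that a liver signal would be hidden across the safety plan. The documents do not support that: 9(h) compares ALT and AST as well, and the stopping and reporting rules (Protocol 6.13 and 8.2.4) combine ALT with bilirubin and the direct fraction, falling back on dipstick or total bilirubin only where fractionation is unavailable. SAP 9(h) itself draws no hepatic conclusion from bilirubin.

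**The fall is a real effect of the switch.** True. The pooled comparison is valid for the switch strategy and should stay. The error would be to read it as hepatic evidence.

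**Few such participants may exist.** Possible. The share is not given, and any stable suppressive regimen qualifies. The exemption arrived with protocol 4.0 (1 July 2020), whereas SAP 6.1 expected everyone to reach week 48 by May 2021, which implies enrolment ending around June 2020. Those dates were only anticipated, however, and criterion 25 never barred elevations below grade 3. Baseline treatment data will settle the share.

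**Conclusion.** The concern holds for the mean comparison of total bilirubin at weeks 24 and 48. With atazanavir shares of 5–20%, an atazanavir baseline mean of 30–50 µmol/L and a true rise of 2 µmol/L, all of them assumptions, the model estimate drops from +2 to between about +1 and −6 to −7. The rank test keeps the sign but can lose much of its power, most severely near a 20% share. At a share near zero the problem disappears. It does not extend to week 96, to ALT or AST, or to the individual rules based on direct bilirubin, and it does not invalidate the pooled result as an effect of switching.

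**What to change.** Keep the pooled comparison in 9(h), labelled as the effect of the switch strategy. Add a prespecified between-arm comparison of total bilirubin at weeks 24 and 48 in participants not taking atazanavir at baseline, using the same model and fallback. Show atazanavir users separately by arm. State that any hepatic reading of bilirubin rests on the non-atazanavir comparison. Leave the ALT and AST analyses as they are.

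The cost is one sentence and one table from data already collected, with slightly fewer participants in the added comparison.
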